- For patients with bilobar involvement, each lobe must be treated separately. A catheter is placed in a lobar hepatic artery for total embolization. The second session should be performed on the other lobe.
- The use of a microcatheter is recommended in case of localized disease in order to obtain an ultra-selective positioning

Patients with localized lesion(s) should be treated with an even distribution of the dose of doxorubicin or streptozotocin within the lesion(s). If possible, chemoembolization should be repeated in the same manner. The two sessions should be separated by 4 to 8 weeks.

For patients with bilobar involvement, each lobe should be treated separately. A catheter is placed in a lobar hepatic artery and the full dose of doxorubicin/lipiodol or streptozotocin/lipiodol is administered. The second session should be performed in the other lobe.

Embolization or chemoembolization must always be associated with appropriate analgesic treatment, prophylactic antibiotic therapy and/or premedication with corticosteroids, the modalities of which are left to the discretion of the investigator.

Repeat chemoembolization sessions:

Three sessions are planned with intervals of 6 to 8 weeks.

The second and third session will be performed depending on the initial tumor response. An additional session is not recommended in case of complete lipiodolated fixation of all tumor targets.

In case of bleeding and/or severe liver failure secondary to an embolization or chemoembolization session, the following session(s) will be cancelled. For any other toxicity secondary to a TACE session, the performance of one (or two) additional sessions will be left to the discretion of the investigator.

Lipiodol and doxorubicin or streptozotocin are reported to health authorities as non-investigational drugs.

However, the tolerance of 2 embolization or chemembolization sessions will be collected in the observation booklet.

2- Everolimus treatment

Everolimus, an investigational treatment, is being provided as part of the study. It will be supplied in boxes of 30 tablets. The tablets will be either 10 mg or 5 mg. The boxes will be labeled "clinical trial" as recommended.

The dosage is 10 mg/day, i.e. 1 tablet of 10 mg or 2 tablets of 5 mg. In case of toxicity, refer to paragraph VII for dose adjustments.

Everolimus treatment will be continued for a maximum of 24 months after the first embolization or chemoembolization.

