syndrome, somatostatin analogue therapy is not permitted after embolization or chemoembolization.

VII. EXPECTED TOXICITIES AND DOSE ADJUSTMENT

1. Dose adjustment after the first embolization or chemoembolization

No dose adjustment of doxorubicin or streptozotocin is planned for chemoembolization sessions. There are no plans to adjust the dose of lipiodol for embolization sessions.

Embolization or chemoembolization will only be performed if hematological, renal and hepatic functions are satisfactory i.e. if:

- PNN $\geq 1.5 \times 10^9$ /L,
- Platelets $\geq 75 \times 10^9$ /L
- Hemoglobin ≥ 10 g/dL
- INR $< 1.3N$ or < 3 on anticoagulants or PT ≥ 50
- Creatinine level $\leq 1.5N$
- Total bilirubin $< 1.5N$
- ASAT, ALAT $\leq 5N$
- PAL $< 5N$

In case of grade 3 or 4 non-hematological toxicity attributable to the first embolization or chemoembolization session, no further embolization or chemoembolization is performed. Only everolimus will be continued for a maximum of 24 months.

2. Everolimus dose adjustment

All toxicity will be assessed according to the NCI-CT v4.0 scale (Appendix 4).

The rules for everolimus dose adjustment in case of observed hematological and non-hematological toxicities are defined in Tables 1.1, 1.2.

All interruptions or changes to the study drug must be recorded

Monitoring of suspected everolimus toxicity

Patients whose treatment is temporarily or permanently discontinued due to an adverse event or laboratory abnormality suspected to be related to everolimus should be monitored at least weekly until the adverse event resolves or returns to grade 1. If the patient's treatment is to be delayed for more than 21 days from the day of the next scheduled dose, the patient should be excluded from the study.

Table 1.0 Guidelines for Everolimus Dose Level Changes

Dose level	Dose and frequency of administration
0 (initial dose)	10 mg per day
-1	5 mg per day
-2	5 mg every 2 days

a. **Dose adjustment for non-hematologic and hematologic toxicities**

Table 1-1 Dose adjustment criteria for everolimus toxicity and reinstatement of everolimus therapy

NON-HEMATOLOGICAL AND NON-HEPATIC Toxicity (NCI-CTC V4.0)	Actions

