* All hepatitis B reactivations should be recorded as a Grade 3 adverse event (CTCAE v 4.0 Other Adverse Events Associated with Metabolic or Biological Abnormalities: Viral Reactivation), unless the investigator considers them life-threatening in which case they should be recorded as a Grade 4 adverse event (CTCAE v 4.0 Other Adverse Events Associated with Metabolic or Biological Abnormalities: Viral Reactivation). The date of viral reactivation is the date on which **both** the DNA and ALAT criteria are met (e.g., for a patient with HBV DNA positive on 01-01-10 and an ALAT level $\geq 5 \times$ ULN on 01-04-10, the date of viral reactivation is 01-04-10).

• Hepatitis C Outbreak Surveillance

The following two categories of patients should be monitored every 6 weeks for HCV reactivation:

- Patients with detectable HCV RNA by PCR analysis in basal state.
- Patients with a known history of hepatitis C virus (HCV) infection, despite a negative baseline viral load test (including those who have been treated and considered "cured")

For the definition of hepatitis C reactivation and guidelines for its management, see Table 2-3 Guidelines for the Management of Hepatitis C.

Table 2-3: Guidelines for the Management of Hepatitis C

HCV outbreak	
For patients with baseline results: detectable HCV RNA, an HCV outbreak is defined as follows:	Discontinue study drug but continue monitoring as part of the study.

Increase in HCV RNA by $2 \log_{10}$ IU/ml AND ALT elevation: $5 \times$ ULN or $3 \times$ baseline, whichever is higher
	

For patients with baseline results: Known history of hepatitis C without detectable HCV RNA, an HCV outbreak is defined as: New appearance of detectable HCV RNA AND ALT elevation: $5 \times$ ULN or $3 \times$ baseline, whichever is higher
	
Discontinue study drug but continue monitoring as part of the study. .

* All hepatitis C outbreaks should be recorded as a Grade 3 event (CTCAE v 4.0 Other Adverse Events Associated with Metabolic or Biological Abnormalities: Viral Outbreak), unless the investigator considers them life-threatening, in which case they should be recorded as a Grade 4 event (CTCAE v 4.0 Other Adverse Events Associated with Metabolic or Biological Abnormalities: Viral Outbreak)

VIII. PATIENT MONITORING DURING TREATMENT AND AFTER WITHDRAWAL OF TREATMENT

1. Monitoring during treatment

Within 7 days prior to each embolization or chemoembolization session

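### Protocol VI.1 plans three chemoembolization sessions against a cap of two and does not defer to the VII.1 toxicity ban; separately, Protocol III restricts three hepatitis B markers to HBsAg-positive patients while the examination schedule does not

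*Protocol*

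**What the plan says.** **Sessions.** The paragraph of Protocol VI.1 headed Repeat chemoembolization sessions says "Three sessions are planned with intervals of 6 to 8 weeks" and continues "The second and third session will be performed depending on the initial tumor response". It adds "An additional session is not recommended in case of complete lipiodolated fixation of all tumor targets". The synopsis (Study design and treatment plan) and the opening of VI.1 allow at most two sessions and require the number to be settled before inclusion and written in the multidisciplinary meeting report. VI.1 elsewhere speaks of two sessions, 4 to 8 weeks apart, and has the observation booklet collect tolerance of two. Protocol VI.2 gives an everolimus stop-and-restart rule for a second session only. SAP 5.2 has one or two sessions.

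**Toxicity.** The same VI.1 paragraph has one mandatory rule: "In case of bleeding and/or severe liver failure secondary to an embolization or chemoembolization session, the following session(s) will be cancelled". It then says "For any other toxicity secondary to a TACE session, the performance of one (or two) additional sessions will be left to the discretion" (the investigator's). Protocol VII.1 says "In case of grade 3 or 4 non-hematological toxicity attributable to the first embolization or chemoembolization session, no further embolization or chemoembolization is performed". VII.1 also sets laboratory conditions: "Embolization or chemoembolization will only be performed if hematological, renal and hepatic functions are satisfactory". Protocol VIII.1, under "Within 7 days prior to each embolization or chemoembolization session", asks for laboratory tests and a review of how the previous session was tolerated.

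**Hepatitis B (a separate matter).** Protocol III requires HBsAg, and the other three markers (HBV DNA, anti-HBs, anti-HBc) only if HBsAg is positive. The examination and follow-up schedule lists all four before treatment with no condition. Tables 2-1 and 2-2 prescribe actions for some HBsAg-negative patients, and VIII.1 calls for HBV DNA every 3 or 6 weeks depending on the result. SAP 7.2.4 describes the three further markers only for HBsAg-positive patients.

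**The concern.** These are instructions to sites on patient safety, and the protocol gives no order of precedence among them.

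A site working from the repeat-session paragraph could give a third chemoembolization that the synopsis does not authorise. It could also use its discretion to repeat the procedure after a serious toxicity for which VII.1 rules that out. VI.1 says chemoembolization is to be preferred to simple embolization, so the paragraph concerns the favoured technique.

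A site working from Protocol III would not look for past or occult hepatitis B in HBsAg-negative patients before starting a drug for which Protocol VII.2.b reports hepatitis B reactivation. Hepatitis B is not itself a non-inclusion criterion, so such patients can enter the trial.

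**Working it through.** **1. Number of sessions.** Inputs: 3 planned (VI.1, repeat sessions); cap of 2 (synopsis; VI.1 opening); patient's own plan of 1 or 2 (SAP 5.2).

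- Above the cap: 3 - 2 = 1 session.
- Above a one-session plan: 3 - 1 = 2 sessions.
- Where the VII.1 ban applies after the first session, 1 is permitted. VI.1 contemplates one or two more, so up to (1 + 2) - 1 = 2 are barred.

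**2. Response as the trigger.** Only sessions two and three depend on response. VI.1 and the schedule footnote keep the CT before session two for technical purposes and exclude it from response evaluation. The first evaluation CT is due 3 months (+/- 1 week) after the first session. At the SAP's 30.4375 days per month, the earliest date is 3 x 30.4375 - 7 = 84.3 days. A second session at 6 to 8 weeks falls on days 42 to 56, before any scheduled response assessment. The trigger fits the CT rule only if Lipiodol fixation is meant as a technical check, which the text does not say.

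**3. Interval.** 6 to 8 weeks lies inside 4 to 8 weeks, so there is no conflict here.

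**4. Toxicity rules side by side.**

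| Event after session one | VI.1, repeat sessions | VII.1 |
|---|---|---|
| Bleeding or severe liver failure | Later sessions cancelled | No further session if grade 3-4, non-haematological and attributable |
| Other grade 3-4 non-haematological toxicity attributable to session one | Investigator decides | No further session |
| Any other toxicity | Investigator decides | Laboratory thresholds only |

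The middle row is the gap. The laboratory thresholds do not close it, because a grade 3-4 event that has resolved, or that those tests do not measure, passes them.

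**5. Hepatitis B branches lost under Protocol III.** Table 2-1 prints one antibody label twice; I read the second as anti-HBc, as in Table 2-2.

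- HBsAg negative, DNA positive: Table 2-1 asks for prophylaxis and 6-weekly DNA. Under section III, DNA is not tested.
- HBsAg negative, DNA negative, with anti-HBc, or anti-HBs without vaccination: Tables 2-1 and 2-2 ask for 3-weekly DNA and define reactivation. Under section III, the antibodies are not tested.
- HBsAg positive: prophylaxis whatever the DNA result. Section III identifies these patients.

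The 3-weekly schedule in VIII.1 corresponds only to the second group, which section III never finds.

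**6. Prophylaxis lead time.** Day 0 is the first session. Table 2-1 asks for a start 1 to 2 weeks before the first everolimus dose.

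- Everolimus on day 7: 7 - 14 = day -7 to 7 - 7 = day 0.
- Everolimus at the day 30 limit: 30 - 14 = day 16 to 30 - 7 = day 23.

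Only for HBsAg-negative, DNA-positive patients does this make the DNA result decisive. With a day 7 start, it is needed by the first session.

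**7. Design figures.** With 68 evaluable patients and success at 31 or more, the exact one-sided alpha at 35% is 0.0461 and the power at 50% is 0.8019. 68 / (1 - 0.05) = 71.6, rounded up to 72. The plan's figures reproduce, and neither session count nor serology enters them.

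**The case against.** The strongest reply is that the repeat-session paragraph is an isolated outlier. The cap is explicit in two places, each patient's plan is written down before inclusion, and VI.2, SAP 5.2 and the rest of VI.1 all assume two sessions. A third session would contradict the patient's own plan. This lowers the practical risk but does not reconcile a plan of three with a maximum of two.

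On toxicity, a reader might infer that the two rules cannot both be followed. The documents do not support that. Discretion includes giving no further session, so a site that obeys VII.1 breaches nothing in VI.1. Nor are the safeguards laboratory-only: VIII.1 requires a review of tolerance before each session, which should bring a resolved event to light. Both points stand. What remains is that no text says which rule governs once the event is known.

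On hepatitis B, a reader might infer that every patient's HBV DNA must be known by the first session. It need not be: HBsAg-positive patients receive prophylaxis regardless of DNA, and HBsAg-negative, DNA-negative patients receive none. Timing is also largely provided for, since Protocol III and the schedule both place serology in the pre-inclusion work-up. The defect is the condition on HBsAg.

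A reader might also fear for the session data. SAP 7.6.1 cross-tabulates planned against performed sessions without a ceiling. Only its per-patient rows and the booklet stop at two, and the everolimus restart delay is described only after sessions one and two. That is minor.

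**Conclusion.** Both points hold, and they are independent of each other.

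The repeat-session paragraph of Protocol VI.1 contradicts the cap and the requirement to fix the number in advance. Its literal effect is one session above the cap, or two above what is permitted where one session was planned or the VII.1 ban applies. Its toxicity discretion lacks a statement that VII.1 prevails: a missing order of precedence, not two rules that exclude each other.

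Protocol III departs from the examination schedule, Tables 2-1 and 2-2 and the monitoring in VIII.1. It would leave HBsAg-negative patients who need DNA monitoring, or prophylaxis if DNA-positive, unidentified.

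The conclusion assumes that some sites work from VI.1 or Protocol III as written; a site that follows the synopsis, VII.1 and the schedule is not exposed. The number of patients affected cannot be derived from the documents. Correction is still required, because the instructions bear on repeating an invasive procedure and on screening before an immunosuppressive drug.

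**What to change.** **Protocol VI.1, repeat sessions.** Amend the paragraph; do not delete it.

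- State at most two sessions, 4 to 8 weeks apart, with the number fixed before inclusion.
- Remove the third session and the allowance of one or two additional ones.
- Remove the dependence on tumor response.
- Keep the cancellation rule for bleeding or severe liver failure, and the advice against a further session after complete Lipiodol fixation.
- Make the investigator's discretion for other toxicity subject to the VII.1 ban and laboratory thresholds.

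**Protocol III.** Make HBsAg, HBV DNA, anti-HBs and anti-HBc unconditional, as in the examination schedule, with results available before the first session. Align the descriptive list in SAP 7.2.4 where the data are collected; the case report form is not among the documents.

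**Cost.** Text corrections to two protocol sections, a letter to sites and one wording change in the SAP. Sites that follow the schedule have no extra test; sites that follow Protocol III add three markers in HBsAg-negative patients. Sample size and efficacy analyses do not change.

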Everolimus will be started 7 days after embolization or chemoembolization or when liver toxicities have returned to a grade ≤ 1 according to the NCI CTIC version 4.0 toxicity scale. Treatment should not be initiated beyond 30 days after embolization or chemoembolization.

If embolization or chemoembolization cannot be performed after patient inclusion, everolimus MUST NOT be started.

If embolization or chemoembolization is postponed, wait for embolization or chemoembolization to start everolimus as described above. If embolization or chemoembolization is definitely cancelled, DO NOT ADMINISTER everolimus and follow the patient according to the recommendations (see paragraph VIII-2: monitoring after cessation of treatment).

For the second session, everolimus will be stopped the day before the session and restarted in the same manner as initially, i.e., 7 days after embolization or chemoembolization or when liver toxicities have returned to a grade ≤ 1 according to the NCI CTIC toxicity scale version 4.0 and within a maximum of 30 days after embolization or chemoembolization.

Method of administration

Everolimus should be taken orally once a day at the same time each day, with or without food. The tablets should be swallowed whole with a glass of water. The tablets should not be chewed or crushed.

If a dose is missed, the patient should not take an additional dose, but should take the next prescribed dose.

3- Concomitant treatments to be avoided

Everolimus is a substrate of CYP3A4 and a moderate inhibitor of P-glycoprotein (PgP). Therefore, the absorption and subsequent elimination of everolimus may be influenced by drugs that act on CYP3A4 and/or PgP. In vitro, everolimus is a competitive inhibitor of CYP3A4 and a mixed inhibitor of CYP2D6.

Known and theoretical interactions with selective inhibitors and inducers of CYP3A4 and PgP are described in the Table below.

CYP3A4 and PgP inhibitors that may increase everolimus concentrations: CYP3A4 or PgP inhibitors may increase blood levels of everolimus by decreasing the metabolism or efflux of everolimus from intestinal cells.

CYP3A4 and PgP inducers that may decrease everolimus concentrations: Substances that are CYP3A4 and PgP inducers may decrease blood levels by increasing everolimus metabolism or efflux of everolimus from intestinal cells.

Effect of other active substances on everolimus

Active substances by interaction	Recommendations for Concomitant Administration
Potent CYP3/PgPA INHIBITORS	

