Ketoconazole	
Itraconazole, posaconazole, voriconazole	
Telithromycin, clarithromycin	
Nefazodone	Concomitant administration of everolimus not recommended
Ritonavir, atazanavir, saquinavir, darunavir, indinavir, nelfinavir	
Moderate CYP3A4/PgP INHIBITORS	

Erythromycin	Use with caution when concomitant administration with moderate CYP3A4 or PgP inhibitors cannot be avoided. If co-administration with a moderate CYP3A4 or PgP inhibitor is required, a dose reduction to 5 mg daily and 5 mg every other day may be considered. However, there is insufficient clinical data on dose adjustment. Due to inter-subject variability, the recommended dose adjustments may not be optimal for all individuals, so close monitoring for adverse effects is recommended.
Verapamil	
Ciclosporin oral	
Fluconazole	
Diltiazem	
Amprenavir, fosamprenavir	
Grapefruit juice or other foods that affect CYP3A4/PgP	The combination should be avoided

Potent CYP3/PgPA INDUCTORS	
Rifampicin	Avoid concomitant use with strong CYP3A4 inducers. If co-administration with a strong CYP3A4 inhibitor is required, an everolimus dose increase of 10 mg daily up to 20 mg daily, using a 5 mg step increase, is applied on day 4 ^{ième} and day 8 ^{ième} after initiation of inducer therapy. This dose of everolimus is established to adjust the AUC to the range of values observed without inducer. However, there are no clinical data available with this dose adjustment. When treatment with the potent inducer is stopped, the dose of everolimus should be returned to the dose used prior to initiation of concomitant administration.
Corticosteroids (e.g. dexamethasone, prednisone, prednisolone)	
Carbamazepine, Phenobarbital, Phenytoin	
Efavirenz, Nevirapine	
St. John's wort (Hypericum Perforatum) with an effect on CYP3A4/PgP	Preparations containing St. John's wort should not be used during everolimus treatment

The use of live vaccines should be avoided during everolimus treatment (examples of live vaccines: intranasal influenza vaccine, measles vaccine, mumps vaccine, rubella vaccine, oral polio vaccine, BCG (Bacillus Calmette-Guérin), varicella vaccine, and Typhoid Ty21a vaccine)

4- Treatment with somatostatin analogues

In patients who were receiving somatostatin analogue therapy for symptomatic purposes prior to embolization or chemoembolization, this therapy should be continued after embolization or chemoembolization unless determined by the investigator. In the absence of carcinoid

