2. For more severe toxicity (grade 2, in which case patients are able, despite pain, to maintain adequate oral nutrition, or grade 3 in which case patients cannot maintain adequate oral nutrition), the proposed treatments are **analgesic topical oral treatments (i.e., local anesthetics such as benzocaine, butylaminobenzoate, tetracaine hydrochloride, menthol, or phenol)** with or without **topical corticosteroids**, such as triamcinolone acetonide 0.1% gingival paste (Orabase Kenalog®).
3. Agents containing hydrogen peroxide, iodine and thyme derivatives may tend to exacerbate mouth ulcers. It is best to avoid these agents.
4. Antifungal agents should be avoided unless a fungal infection has been diagnosed. In particular, systemic imidazole antifungal agents (ketoconazole, fluconazole, itraconazole, etc.) should be avoided in all patients as they are potent inhibitors of everolimus metabolism, resulting in higher everolimus exposures. Therefore, topical antifungal agents are preferable if an infection is diagnosed. Similarly, antiviral agents such as acyclovir should be avoided unless a viral infection is diagnosed.

d. Management of hyperlipidemia and hyperglycemia

Hyperlipidemia and hypertriglyceridemia should be treated according to local best clinical practice.

e. Management of non-infectious lung disease

Non-infectious pneumonitis is a class effect of rapamycin derivatives. Non-infectious lung disease (including interstitial lung disease) has also been described in patients treated with everolimus. A diagnosis of non-infectious lung disease should be considered in patients presenting with non-specific respiratory signs and symptoms such as cough or dyspnoea, hypoxia, pleural effusion, and when infectious, neoplastic or other non-drug causes have been excluded by appropriate investigations. Patients should be asked to report promptly any new or worsening respiratory symptoms.

Patients with radiological changes suggestive of non-infectious lung disease with few or no symptoms may continue everolimus therapy without a change in dosage. In the presence of moderate symptoms (Grade 2), discontinuation of treatment should be considered until symptoms improve. Administration of corticosteroids may be indicated. Everolimus may be reintroduced at a reduced dose until recovery to Grade 1 or higher.

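### Protocol VI.3: the rule raising everolimus to 20 mg daily names a strong CYP3A4 inhibitor where only a strong inducer fits

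*Protocol*

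**What the plan says.** Protocol VI.3 first gives the direction of each interaction. For inhibitors: "CYP3A4 or PgP inhibitors may increase blood levels of everolimus". For inducers: "Substances that are CYP3A4 and PgP inducers may decrease blood levels by increasing everolimus metabolism".

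The table that follows has a block for each class:

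- **Potent inhibitors** (ketoconazole, clarithromycin, ritonavir and others): "Concomitant administration of everolimus not recommended".
- **Moderate inhibitors** (erythromycin, verapamil, fluconazole and others): where the combination is needed, "a dose reduction to 5 mg daily and 5 mg every other day may be considered".
- **Potent inducers** (rifampicin, carbamazepine, phenytoin and others): these are to be avoided. Then comes the rule at issue: "If co-administration with a strong CYP3A4 inhibitor is required, an everolimus dose increase of 10 mg daily up to 20 mg daily". The increase is made in 5 mg steps on the fourth and eighth days, counted from the start of the inducer. Its purpose is then given: "This dose of everolimus is established to adjust the AUC to the range of values observed without inducer". Once the inducer is stopped, the patient goes back to the previous dose.

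Protocol VII.2.c, on stomatitis, returns to the subject. It says that systemic imidazole antifungals "should be avoided in all patients as they are potent inhibitors of everolimus metabolism, resulting in higher everolimus exposures".

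**The concern.** This is an operative dosing instruction for the investigational drug, not background text. Its trigger is a class of drug that, by the protocol's own account, raises everolimus exposure, and its action is to raise the dose. Taken by itself, the opening clause points the investigator in the wrong direction.

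There is a second, quieter consequence. Because the trigger names an inhibitor, the block no longer says when the increase applies to a patient who must take a strong inducer, which is the case the rule was evidently written for.

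**Working it through.** The plan gives no statistical figure to reproduce here, so the check is mainly a comparison of texts.

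**1. Direction of effect.** By the introductory paragraphs of VI.3, an inhibitor moves everolimus levels up and an inducer moves them down. A dose increase offsets a fall in exposure and adds to a rise. It therefore fits an inducer and does not fit an inhibitor. VII.2.c gives the same direction for potent inhibitors.

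**2. The block itself.** Five elements around the disputed word all refer to inducers:

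- the heading of the block;
- the sentence immediately before, which tells the reader to avoid strong inducers;
- the timing clause of the same sentence, which counts days from the start of the inducer;
- the rationale, which aims at the AUC seen without an inducer;
- the stopping rule, which applies when the inducer ends.

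The sentence is thus inconsistent within itself: its trigger is an inhibitor and its clock starts with an inducer.

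**3. The inhibitor rows.** The potent-inhibitor row covers the class that the sentence names and advises against the combination. That is a direct conflict. The moderate-inhibitor row covers another class, so it does not contradict the sentence directly. It only shows again that the protocol moves the dose down, not up, when an inhibitor is present.

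**4. The dose steps.** Starting dose 10 mg daily (VI.2), step 5 mg, two steps:

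- day 4: 10 + 5 = 15 mg daily;
- day 8: 15 + 5 = 20 mg daily.

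This agrees with the stated upper dose of 20 mg daily. The figures are consistent and stay the same when the word is corrected.

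**5. Reach into the statistics.** The sample size (68 evaluable, 72 included) and the SAP decision rule (31 or more of 68 patients alive without liver progression at 24 months) do not use this sentence.

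**The case against.** The strongest reply is that the sentence can hardly be carried out as written. A patient taking a strong inhibitor and no inducer has no inducer start date, so days 4 and 8 cannot be counted. An investigator who looks up ketoconazole or clarithromycin finds it in its own row, with advice against the combination. The intended word is plain from the rest of the cell. All of this stands, and it is why the practical risk is low.

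The slip may also have arisen in translation, since the public text reads as a translated document. The documents cannot settle this. The sentence is nevertheless complete, current protocol text, and not a damaged table cell or a redaction.

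Some readers might infer more than the documents support:

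- **That patients on strong inhibitors would be escalated to 20 mg.** The inducer-based schedule largely blocks this. The documents also give no number of patients taking such drugs, so no count of those exposed can be made.
- **That the size of the error can be read from dose ratios.** A comparison with the table headed "Table 1.0 Guidelines for Everolimus Dose Level Changes" fails because that table is a ladder for reducing the dose after toxicity, not a ceiling for interactions. The corrected rule still reaches 20 mg. A comparison with the moderate-inhibitor row sets one drug class against another, and the reduction there is only an option, which the protocol says rests on insufficient clinical data.
- **That sites worked from the wrong word.** Only the source-language version could show this.

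**Conclusion.** The word is wrong as written, and the protocol alone proves it. The sentence conflicts with the stated direction of effect in VI.3 and VII.2.c and with the potent-inhibitor row. Every other element of its own block calls for an inducer.

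Severity is minor. The point deserves correction because it concerns dosing of the study drug, and because the correction restores the trigger for a strong inducer that cannot be avoided. It does not show that any patient was, or would be, dosed wrongly. The conclusion rests on no numerical assumption. The one unknown is whether the version used at sites has the same word.

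**What to change.** In the potent-inducer block of VI.3, change inhibitor to inducer in the sentence that introduces the increase to 20 mg daily. Leave the dose, the steps and the days as they are. Check the same sentence in the source-language protocol used at sites. If the slip is there too, notify the sites.

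The cost is one word and, if needed, one site letter. Data collection, sample size and analysis do not change.
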